
The drug for this submission is Hope Biosciences' allogeneic, adipose-derived culture-expanded mesenchymal stem cells (HB-adMSCs) to treat COVID-19. We hypothesize that the immunomodulatory properties of MSCs will inhibit cell-mediated immune inflammatory responses and MSC endogenous regenerative properties will reduce pathological changes of lung associated with COVID-19. The population we are proposing to treat are suspected to be positive

for COVID-19, which will be confirmed by testing during the trial. We have preclinical safety and efficacy data, as well as clinical evidence of the safety of HB-adMSCs in patients in ongoing phase I/IIa clinical trials for Rheumatoid Arthritis (NCT03691909), Traumatic Brain Injury and/or Hypoxic-Ischemic Encephalopathy (NCT04063215), and Alzheimer's Disease (NCT04228666), as well as individual expanded access for Parkinson's Disease (NCT04064983), Spinal Cord Injury (NCT04064957 and NCT03925649), and Cerebral Palsy (NCT04029896). We have experience with an individual expanded access for Pancreatic Cancer (NCT04087889) who received allogeneic HB-adMSCs, as well. All treatments have been well-tolerated, with no severe adverse events related to the study drug.

Study Objectives and Endpoints

Study Objectives

Primary:

- To investigate the safety and efficacy of HB-adMSCs as a treatment for patients suspected to have COVID-19.

Secondary:

- To investigate the safety and efficacy of HB-adMSCs in improving clinical status of patients suspected to have COVID-19 infection.

Study Endpoints

Primary:

- change from baseline in inflammatory markers (TNF-alpha, IL-10, IL-6, C-Reactive protein)
- change from baseline oxygenation
- Time to return to room air (RTRA)

Secondary:

- Change in clinical laboratories
- Change from baseline Chest X-ray
- Change from baseline CT scan
- Change from baseline in exploratory markers (D-dimer, myoglobin, troponin, creatinine kinase, serum ferritin, CD3CD56, CD4/CD8, VEGF)
- Time to negative PCR test results
- Change from baseline in the 7-point ordinal scale
- Cumulative incidence of serious adverse events (SAEs) or adverse events (AEs)

Investigational Plan

This Phase II, randomized, placebo-controlled, double-blinded, trial assesses efficacy in a population of hospitalized patients to evaluate efficacy of HB-adMSCs to treat Coronavirus Disease. It is designed to be conducted in 2 arms:

Consenting patients will be randomly assigned to one of two arms:

Arm 1 (HB-adMSCs) (n=60)

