Patients will receive four intravenous infusions of 100 million HB-adMSCs throughout the entire duration of the study.

Arm 2 (placebo) (n=40)

Patients will receive four intravenous infusions of placebo (saline solution) throughout the entire duration of the study.

Safety assessments will be ongoing. Safety tests will include EKG, Complete Blood Count with differential, Complete Metabolic Profile (to include renal function and hepatic function) and Coagulation Panel screening for hepatotoxicity, cytopenias, renal failure or alterations in the coagulation cascade that might entail a safety concern for the individual. Efficacy will be measured by change from baseline in inflammatory markers (IL-6, CRP, IL-10, TNF-alpha), change from baseline in oxygenation, and time to receive negative PCR test result, change from baseline in exploratory markers (D-dimer, myoglobin, troponin, creatinine kinase, serum ferritin, CD3CD56, CD4/CD8, VEGF), time to return to room air (RTRA), change from baseline chest x-ray, change from baseline CT scan, and change from baseline in 7-point ordinal scale.

Selection and Withdrawal of Patients

Inclusion Criteria

1. Men, and women, over 18 years of age inclusively.
2. Suspected COVID-19 infection
3. Provides consent or consent is given by their legally authorized representative (LAR)
4. Agrees to the collection of venous blood per protocol.

Exclusion Criteria:

1. Pregnancy, lactation and those who are not pregnant but do not take effective contraceptive measures, in women of childbearing age.
2. Patients who have participated or are participating in a clinical trial of an experimental vaccine for SARS-CoV-2 or coronavirus during the study or within 30 days.
3. Inability to provide informed consent or to comply with test requirements.

4. Any medical disease or condition that, in the opinion of the site Principal Investigator or sub-investigator, precludes study participation. Including acute, subacute, intermittent or chronic medical disease or condition that would place the subject at an unacceptable risk of injury, render the subject unable to meet the requirements of the protocol, or may interfere with the evaluation of responses or the subject's successful completion of this trial.

Withdrawal, Removal, and Replacement of Patients

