Patients will be considered to have completed the study if they complete treatment and assessments through day 28. A patient's investigational treatment should be discontinued if any of the following situations occurs:

- The Investigator believes that for safety reasons, it is in the best interest of the patient to stop treatment.
- The patient is non-compliant with the study visit schedule or other protocol requirements.
- The patient develops a severe allergic reaction that occurs following investigational product administration.

A patient may voluntarily withdraw or be withdrawn from the study at any time for reasons including, but not limited to, the following:

- Patient withdrawal of consent: At any time, a patient's participation in the study may terminate at his/her request. The specific reason for patient withdrawal will be noted on the case report form (CRF).
- Lost to follow-up: The patient stops coming for visits, and study personnel is unable to contact the patient after repeated attempts (e.g., mail, or email).
- This study may be terminated at the discretion of the Sponsor or any regulatory agency.

If a patient's infusions are discontinued at any point during the trial and the patient maintains consent to contribute additional outcome information, the patient should continue to be followed through day 28 for all safety and efficacy assessments. Investigators will be trained about the importance of retention and steps to prevent missing data. The date and reason for withdrawal are to be documented in the CRF. The study site(s) must immediately notify the medical monitor. The patients who withdraw prematurely must attend an early discontinuation visit if possible, at which time they will complete all assessments described in Table 2 under day 28. Unless the patient declines (consent withdrawn), the follow up phone call at day 28 should be done in all patients who were enrolled in the study regardless of their enrollment status.

In the event that a patient discontinues prematurely from the study due to an Adverse Event (AE) or serious AE, the event will be followed until it resolves (returns to normal or baseline values) or stabilizes, or until it is judged by the Investigator to be no longer clinically significant. Once a patient is withdrawn from the study, the patient may not re-enter the study.

Treatments

Details of the investigational product

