If a patient is screened and fails to meet any study entry criteria or falls outside the screening window, they may be re-screened only once. Such patient must be fully consented a second time before the second set of screening assessments take place and shall be assigned a new subject number. Investigator discretion should be exercised in determining who may be re-screened.

In case of doubt about the accuracy of screening laboratory value(s), the laboratory test(s) may be repeated provided that this can be done within the 7-day screening period without the need to repeat all other screening procedures (i.e., no re-screening).

If a patient is enrolled after they have been re-screened, such subject shall be assigned a new subject ID number, different from the previous attempt to enroll.

Assessments by Week

Assessments will occur as outlined in the following subsections. For visits at Day 0 through 28 days, there will be a window of ± 3 days.

Screening

The Screening visit will last up to 7 days. Results from laboratory samples collected in this visit will set a baseline. These are the procedures to be performed during this visit:

- Written Informed Consent will be obtained from the subject or their legally authorized representative (LAR).
- COVID-19 confirmatory test results may be in progress during the screening period.
- Demographic Information will be obtained.
- Medical History and Current conditions will be obtained,
- Concomitant Medications will be obtained. Every medication listed should match a condition in the medical history.
- Vital signs will be obtained.
- Weight and Height will be measured.
- A physical exam will be performed.
- Blood and urine samples will be collected for laboratory assessments (CBC with differential, chemistry, and coagulation, pregnancy if appropriate).
- Ascertain patient eligibility by evaluating patient results against the inclusion/exclusion criteria.

Upon completion of all Screening procedures, the Principal Investigator must confirm and document the patient eligibility in the “Screening Result” CRF.

Infusion #1 - Day 0 (Baseline)

- Weight will be measured
- Vital Signs will be measured.
- Concomitant medications will be reviewed and updated if necessary.

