The Bayesian approach addresses these questions: (1) “Among patients with suspected COVID-19, what is the probability that allogeneic HB-adMSC 100mm confers benefit relative to placebo on status on inflammatory markers (C-Reactive protein, TNF-alpha, IL-6, IL-10), change from baseline oxygenation, and time to return to room air (RTRA) at treatment Day 10?” (2) “What is the best estimate of these effects?” and (3) “What is their precision?” By estimating the probability that such effects exist, we are assessing the probability that the alternative hypothesis is true; a probability that is, by definition, not accessible to Frequentist methods. The FDA has discussed the use of Bayesian statistical methods to make decisions regarding the efficacy of new treatments as an alternative to Frequentist methods in developing clinical applications. The current proposal will provide the optimal, unbiased estimates for the benefit conferred by allogeneic HB-adMSC, while also estimating the probability that such effects exist. Posterior distributions can then be used as informative priors for continued monitoring in expansions of treatments and treatment strategies exhibiting initial promise.

Presentation of results from the statistical models will include the estimated conditional/marginal mean treatment effects. For all endpoints analysed statistically, estimated mean treatment differences will be presented together with 95% credible intervals and posterior probabilities,

HB-adMSCs 100MM vs Placebo

All safety evaluations will be presented using Safety Analysis Set. The efficacy analysis will be presented using Efficacy analysis set.

Individual safety and efficacy parameters will be listed.

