## 7. EFFICACY ANALYSES

### 7.1. Primary Efficacy Analyses

#### 7.1.1. Endpoint / Variables

The primary efficacy endpoints are changes from baseline in the following outcomes at each post-baseline visit:

- Inflammatory markers (TNF-alpha, IL-10, IL-6, C-Reactive protein)
- Oxygenation
- Time to return to room air (RTRA) and proportion of patients with room air status

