#### **7.1.4.1. Statistical Methodology Specification**

Initial analyses examining group differences for baseline variables will use cross-tabulation, ANOVAs, and examination of correlations between baseline variables and specified outcomes. For the purposes of evaluating the comparability of groups, a posterior probability of  $\geq 75\%$  will constitute evidence for statistically reliable differences. Baseline or demographic variables on which group differences are detected, and which are correlated with outcomes, meet the definition of confounders and will result in two sets of analyses: one in which only the stratification variables are included as covariates, and another where the relevant variable is included as a covariate. This will permit determination of the degree to which any group differences might confound conclusions regarding treatment. A third set of analyses will model the effect of treatment group (controlling for stratification variables) on each outcome, focusing on the subgroup of patients who survived through the last infusion visit where statistically feasible.

Broadly, the data analytic strategy will use generalized linear, multilevel, and survival/cox proportional hazard models (R v 4.1, 2021; brms v 2.17; RStan v 2.21) for discrete, continuous, and time-to-event outcomes. Multilevel generalized linear modeling to account for clustering of patients within site and repeated observations within patients will evaluate continuous, dichotomous, and count data. All analyses will address potential missingness through joint modeling of observed outcomes and the missing data, an approach robust to ignorable missingness (i.e., MCAR and MAR). Sensitivity analyses will evaluate robustness of analytic conclusions to missing data. Non-ignorable missing data patterns will be addressed through pattern-mixture modeling methods.

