#### **7.1.4.2. Data Analytic Models**

All primary endpoint efficacy measurements available at post-baseline at scheduled measurements (Visits 2 through 5 [infusions 1 through 4] for inflammatory markers, oxygenation, and room air status) will be analysed in a generalized linear mixed model. The model will predict each outcome as a function of the interaction between the fixed factors treatment group and time, controlling for lower order effects of time and treatment group. Models will control for stratification variables (see [Covariates and Other Strata](#)), and subject will be included as random effects.

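### Time to return to room air, a primary endpoint, has no at-risk population and no rule for death, and the efficacy set selects on surviving to the fourth infusion

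*SAP*

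**What the plan says.** **Endpoint.** SAP 7.1.1 lists "Time to return to room air (RTRA) and proportion of patients with room air status" under a lead-in that describes every primary endpoint as a change from baseline at each post-baseline visit. SAP 5.7 frames the question as benefit on "time to return to room air (RTRA) at treatment Day 10". The protocol's Efficacy Analysis section describes the event only as no longer needing supplementation. It gives no start time, no required duration and no censoring rule.

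**Population.** SAP 5.7 and 7.1.3 place the primary efficacy endpoints in the efficacy analysis set. SAP 4 and the protocol's Analysis Population section limit that set to patients who received all four infusions, the last of them scheduled for Day 10. On timing, the protocol's Assessments by Week section says: "For visits at Day 0 through 28 days, there will be a window of ± 3 days". A nominal Day 10 visit can therefore fall anywhere from Day 7 to Day 13.

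**Who is enrolled.** The disease criterion is "Suspected COVID-19 infection"; no criterion concerns oxygen. The Investigational Plan says the trial "assesses efficacy in a population of hospitalized patients". Category 5 of the protocol's 7-point scale is a hospitalised patient who needs no supplemental oxygen, and the Data Safety Monitoring Board section plans a review of the first five patients with mild symptoms.

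**Model and death.** SAP 7.1.4.1 names Cox models for time-to-event outcomes in general, without naming RTRA. SAP 7.1.4.2 puts "Visits 2 through 5 [infusions 1 through 4] for inflammatory markers, oxygenation, and room air status" into a mixed model. The only reference to survival in the efficacy analysis is a third set of analyses "focusing on the subgroup of patients who survived through the last infusion visit where statistically feasible" (SAP 7.1.4.1). The missing-data text does not mention death.

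**The concern.** A time-to-event endpoint needs a population that can have the event, a time origin, a horizon and a rule for anything that prevents the event. For RTRA only the horizon is stated.

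- **At risk.** A patient on room air at Day 0 cannot return to it. Whether such a patient is an immediate event, a success in the room-air proportion, or outside the analysis is left open. The first two shrink any difference.
- **Death.** Three readings are possible: earlier deaths are excluded (SAP 4), included in some way (implied by the survivor set in SAP 7.1.4.1), or censored (a common default in Cox software). They estimate different things.
- **Form.** A time to event has no baseline value, so it cannot be a change from baseline.

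At stake is a named primary endpoint whose result could depend on choices made after the data are seen.

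**Working it through.** **Plan figure to reproduce.** There is none for RTRA. The protocol sets N = 100 by anticipated demand, with no event rate, effect size or power. The 3:2 ratio does give 60:40. Baseline room-air share, recovery rates and mortality are not in the documents, so every value of these below is an assumption.

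**1. Dilution of the proportion.** Let f be the share on room air at baseline. If they stay on room air in both arms, they contribute no difference, so observed difference = true difference x (1 - f). For an assumed 20 points:

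- f = 0.20: 20 x 0.80 = 16
- f = 0.40: 20 x 0.60 = 12
- f = 0.60: 20 x 0.40 = 8

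**2. Dilution of the hazard ratio (HR) and effect on power.** Assume return by Day 10 in 50% of placebo and 75% of treated patients among those at risk (HR 2.0). The HRs come from simulation (20 runs of 20,000 patients, 3:2), with baseline room-air patients coded as events at time zero. Power is for comparing proportions with 100 randomised.

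| f | HR, everyone | Power, everyone | Power, at risk only |
|---|---|---|---|
| 0 | 2.0 | 73% | 73% |
| 0.20 | 1.65 | 59% | 63% |
| 0.40 | 1.4 | 44% | 51% |
| 0.60 | 1.2 | 30% | 37% |

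Restricting to patients at risk keeps the HR at 2.0. Day 10 events are 60 x 0.75 + 40 x 0.50 = 65 at f = 0, falling to 52, 39 and 26. Cox power is then 78, 69, 56 and 41%; 80% needs 69 events.

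**3. Deaths censored.** Assume a recovery hazard r = 0.08 per day in both arms and death hazards d = 0.01 and 0.04 per day.

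- 1 - KM at Day 10 = 1 - exp(-0.08 x 10) = 0.551 in both arms.
- True cumulative incidence = r/(r + d) x [1 - exp(-(r + d) x 10)].
- d = 0.01: (0.08/0.09) x (1 - exp(-0.9)) = 0.527.
- d = 0.04: (0.08/0.12) x (1 - exp(-1.2)) = 0.466.

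These hazards imply 6.6% and 23.3% dead before return by Day 10, a wide contrast. With milder assumptions (50% return in the absence of death), 1 - KM reads 50% in both arms. True values are 47.7% and 45.4% for Day 10 deaths of 10% and 20%, and 46.6% and 42.9% for 15% and 30%.

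**4. Deaths excluded, as SAP 4 reads.** Use the hazards of step 3 and assume that deaths occur only before return, that the fourth infusion is on Day 10, and that all survivors receive it. The share returned among those retained is cumulative incidence / (1 - deaths):

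- d = 0.01: 0.527/(1 - 0.066) = 0.565
- d = 0.04: 0.466/(1 - 0.233) = 0.607

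The arm with more deaths now looks better, although its true probability of return is lower.

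**5. HR when death and recovery share a cause.** This uses the same simulation size, no true effect on recovery, and a shared severity factor (log-SD 1). HR above 1 favours treatment.

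| Day 10 deaths, control v treated | Deaths censored | Deaths dropped |
|---|---|---|
| 10% v 10% | 1.01 | 1.01 |
| 20% v 10% | 0.97 | 0.92 |
| 30% v 15% | 0.95 | 0.89 |
| 10% v 20% | 1.04 | 1.10 |

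Dropping deaths distorts more than censoring them when mortality differs. With deaths independent of recovery, the censored HR stays at about 1.0 throughout.

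**6. The two SAP sections side by side.** Under SAP 4, a patient who dies before the fourth infusion is not in the efficacy set. A further analysis limited to survivors through the last infusion visit would then remove almost nobody. It has a purpose only if the main analysis contains earlier deaths.

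**The case against.** Several points on the other side stand.

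- A reader might infer that deaths are censored in a Cox model. No section says so; under SAP 4 a death before the fourth infusion is excluded, so few deaths would remain to censor by Day 10.
- A reader might also infer that censoring biases the HR. The cause-specific HR is not biased in itself. If treatment changes mortality but not the recovery hazard, 1.0 is the correct value. Bias needs mortality that differs by arm and shares causes with recovery.
- Nor do the documents support saying that the plan conceals harm. Death is category 1 of the ordinal scale, fatal events are serious adverse events analysed by arm, and the monitoring board reviews all deaths.
- The Day 10 horizon is a stated choice, not a bias. Its costs are fewer events and coarse timing. Although completers are those who "complete treatment and assessments through day 28", the ordinal scale has no scheduled assessment between Days 10 and 28, Day 28 may be a telephone call, and categories 6 and 7 do not record oxygen at home. It cannot date a return in that gap.
- Dilution depends on coding. The protocol's reference to time needing respiratory support points towards patients on oxygen, and SAP 5.4.1 adjusts for illness severity. Patients on room air can also deteriorate, so including them in the proportion is a defensible estimand if declared.

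What does not stand is that these points settle the matter. A severity covariate does not define a risk set, and a hint in the protocol's description is not an analysis rule.

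**Conclusion.** The concern holds as a defect of definition with a measurable effect. RTRA is planned in a set that can include patients unable to have the event, it is listed in a form it cannot take, and death has no rule. SAP 4 and SAP 7.1.4.1 point in different directions on deaths before the fourth infusion.

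If baseline room-air patients are counted, 20 points become 16 to 8 for a share of 20 to 60%; if they are left out of the risk set, there is no dilution. Excluding early deaths selects on a post-randomisation outcome and moved a null HR to between 0.89 and 1.10 in the scenarios tried. Censoring them overstates the probability of return, by about 2 to 8 points across the assumptions used (0.551 - 0.527 and 0.551 - 0.466 at the extremes). All these sizes rest on assumed rates. The documents do not support a firm direction of bias, nor a claim that the Day 10 horizon is itself an error.

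**What to change.** Amend the SAP before the analysis is run:

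1. Analyse time to RTRA in randomised patients on oxygen or ventilation at Day 0 (ordinal categories 2 to 4), without requiring four infusions. The protocol already asks for patients who stop infusions to be followed for all assessments if they consent.
2. Keep Day 10 as the horizon. State the time origin and how long a patient must stay on room air for the event to count.
3. Treat death as a competing event, meaning no return by the horizon, and report cumulative incidence by arm. Give the cause-specific HR beside it, because keeping deaths in the risk set mixes recovery with mortality. In simulation with no effect on recovery and deaths independent of it, that approach gave 1.06 for deaths of 20% control v 10% treated, and 0.93 for the reverse.
4. Count death as not on room air in the proportion. If room-air patients at baseline stay in that measure, declare it as a separate estimand.
5. Reconcile SAP 4 with the survivor analysis in SAP 7.1.4.1.
6. Take RTRA out of the change-from-baseline list in SAP 7.1.1 and name its model.
7. Add Day 28 ordinal status only as a supportive binary outcome, with a stated convention for discharged patients.

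The cost is mainly SAP wording. Fewer patients enter the time-to-event analysis, but those left out cannot have the event, and in the scenarios above power on the proportion rises by 4 to 7 points (63 v 59%, 51 v 44%, 37 v 30%).
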